Injection site reactions	
Most AEs have been mild, transient injection site reactions, including erythema, pain, bruising, pruritus, burning, tenderness, edema, induration, irritation, paresthesia, numbness, and rash. Moderate injection site reactions occurring less frequently include burning, erythema, pain, and numbness.
 
Localized injection site reactions have been observed in studies with efgartigimod and PH20 and administered SC
	
Continuously monitor participants for injection site reactions when treatment is administered on-site.
 
Injection site reactions are considered AEs of clinical interest (Section 8.4.7).

Potential complications from exposure to OCS	
OCS are considered a first-line therapy for patients with moderate-to-severe BP; however, these drugs cause various adverse side effects. Therefore, a therapeutic goal in the treatment of patients with BP is a reduction in OCS exposure.
	
Rapidly taper OCS doses based on the clinical status of the participant (Section 6.3).
 
Continuously monitor safety, including glucocorticoid-mediated toxicity, throughout the study (Section 8.3.6).
 
Provide prophylactic and supportive care to diminish the expected side effects of OCS (ie, antiosteoporotic treatments, calcium supplements and vitamin D) are allowed in the study.

Older adult population	
Patients with BP are typically older adults who can have comorbidities that result in a general poorer condition compared to the general population.
	
The investigator will assess if it is appropriate for the participant to be included in the study (Section 5.2, criterion 1).

AE=adverse event; AESI=adverse event of special interest; BP=bullous pemphigoid; efgartigimod PH20 SC=efgartigimod for SC administration coformulated with rHuPH20; IgG=immunoglobulin gamma; OCS=oral corticosteroid; rHuPH20=recombinant human hyaluronidase PH20; SC=subcutaneous

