Complete remission on minimal OCS therapy (CRmin)	Being in complete remission (CR) for ≥ 8 weeks and have been on minimal OCS therapy (≤ 0.10 mg/kg/day of prednisone or an equivalent dose of another OCS) for ≥ 8 weeks
Complete remission off OCS therapy (CROff)	Being in CR for ≥ 8 weeks and have been off OCS therapy for ≥ 8 weeks.
display	Analysis table, listing, or figure
IMP	Pharmaceutical form of an active ingredient or placebo, being tested or used as a reference in a clinical study.
missing data	Data that would be meaningful for the analysis of a given endpoint but were not collected. They should be distinguished from data that do not exist.
standardized unit	unit populating --STRESU in the clinical database
treatment-emergent abnormality / toxicity	
Any postbaseline* abnormality/toxicity which was not present at the study baseline or worsened after the study baseline (e.g., hemoglobin normal or grade 1 at baseline and grade 2 postbaseline; glucose low at baseline and high postbaseline; QTcF [450; 480] ms at baseline and >500 ms postbaseline). If baseline is missing, any postbaseline abnormality/toxicity will be considered emergent.
 
*Note: postbaseline records on or after the first administration of IMP in ARGX-113-2010 and up to and including 60 days after the last IMP administration before the assessment will be considered for treatment-emergence.

	Statistical Analysis Plan	
ARGX-113-2010	Final analysis	Final 1.0 of 29APR2025

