1.3 STATISTICAL HYPOTHESIS

No formal hypothesis testing will be conducted in this open-label study.

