^a The baseline analysis visit will be assigned to the first phase that is applicable for a participant, either the observation phase or the treatment phase. The baseline visit is defined in section 2.2.2 and does not require definition of analysis visit limits.

^b x increases in steps of 4 weeks (On IMP subperiods) or 8 weeks (observation phase or Off IMP subperiods) up till the point where the upper limit of the analysis visit window exceeds the end day of the phase/subperiod. In this case the upper limit will be cut at the end day of the phase/subperiod. The maximum value of x is week 48.

^c T = target day of current analysis visit, T_n = target day of next window, T_p = target day of previous window.

^d An assessment on AWADY = 1 that is not selected as Baseline/TPnB will be assigned to Week 2.

Baseline and TPnB are defined in section 2.2.2.

Per parameter and analysis visit, the nonmissing value closest to the target AWADY will be used in analysis tables, other values will only be listed. If more than one nonmissing value is located at the same distance from the target, then the one latest in time will be selected for analysis. The value latest in time will be identified using, in order of preference, the assessment date(time), the visit label, the database group identifier or sequence number.

For immunogenicity assessments, the selection will be performed by sample (not by parameter) and analysis visit in order to keep the ADA and NAb results of a sample together. Furthermore, values resulting in an unevaluable ADA status are given the lowest priority when the selection is made.

Missing assessment dates will be imputed with the corresponding visit date. If there is no corresponding visit date available, the assessment will not be allocated to an analysis visit.

2.2.5 *Worst-case*

A worst-case analysis visit will be created for parameters with defined abnormalities and/or toxicity grades (e.g., labs, vital signs, ECGs). For abnormalities, the worst-case is derived per parameter and if both the lowest and highest values are considered abnormal, a participant can have two worst-case analysis visits for the same

	Statistical Analysis Plan	
ARGX-113-2010	Final analysis	Final 1.0 of 29APR2025

parameter. For toxicity grades, the worst-case is the value associated with the highest toxicity grade and is derived per parameter and toxicity direction (hypo/hyper).

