5.2.2 Derivation rules

The following abnormality categories will be defined:

- Low: value < lower limit of normal range
- Normal: lower limit of normal range ≤ value ≤ upper limit of normal range
- High: value > upper limit of normal range

Notes:

- Abnormalities will be derived for hematology and biochemistry parameters for which no toxicity grading is defined.
- Classification will be performed in standardized units, using nonimputed values and limits.
- For the worst-case analysis visit, as defined in section 2.2.5, an additional category low + high is defined if there are both low and high postbaseline values

Toxicity grades will be computed according to the NCI CTCAE toxicity grading list (version 5.0). The implementation of these toxicity grades for analysis is presented in appendix 9.2. Only the parameters described in appendix 9.2 will be computed, according to the declared limits for each grade.

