5.2.3 Presentation of results

The SAF analysis set will be used for the clinical laboratory evaluation. For tables by analysis visit, only the baseline and last assessment analysis visits will be shown. Cross-tabulations will also include the worst-case analysis visit. All other analysis visits will be included in listings.

Only continuous laboratory parameters expected per protocol will be tabulated, except for INR. The statistical analysis will present results in standardized units, except for creatinine clearance (adjusted for BSA), which will be reported in mL/min/1.73m².

Continuous laboratory parameters will be summarized using descriptive statistics at each analysis visit of interest. Actual values and changes from study baseline will be shown in the same table.

Laboratory abnormalities will be presented as cross-tabulations of the abnormality at each postbaseline analysis visit of interest versus the study baseline abnormality. The number of participants with treatment-emergent abnormalities will also be shown (see Definition of terms). The denominator for the percentage is the total number of

	Statistical Analysis Plan	
ARGX-113-2010	Final analysis	Final 1.0 of 29APR2025

participants with nonmissing data for the parameter and analysis visit in the SAF analysis set.

Laboratory toxicity grades will be presented as cross-tabulations of the toxicity at each postbaseline analysis visit of interest versus the study baseline toxicity. Numbers and cumulative numbers over decreasing toxicity grading of participants with treatment-emergent toxicities will also be shown. The denominator for the percentage is the total number of participants with nonmissing data for the parameter and analysis visit in the SAF analysis set. Parameters with toxicity grades defined in both directions (hypo and hyper) will be shown by direction.

All laboratory data will be listed for the ROL analysis set, including laboratory tests not foreseen per protocol, but only for participants with any postbaseline abnormality or toxicity grade ≥ 1 .

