9.2 TOXICITY GRADES

Below Table 8 documents how the Criteria for Adverse Events CTCAE, v5.0: November 27, 2017 is implemented in the statistical analysis.

Table 8: Analysis toxicity grades (CTCAE 5.0)

PARAMETER	Unit	GRADE 1	GRADE 2	GRADE 3	GRADE 4
Amylase (pancreatic) ^c		>1.0-1.5 *ULN	>1.5-2.0 *ULN	>2.0-5.0 *ULN	>5.0 *ULN
Alanine amino transferase ^c		>1-3 *ULN	>3-5 *ULN	>5-20 *ULN	>20 *ULN
Albumin ^a	g/L	<LLN-30	<30-20	<20	-
	g/dL	<LLN-3	<3-2	<2	-
Alkaline phosphatase ^c		>1.0-2.5 *ULN	>2.5-5.0 *ULN	>5.0-20.0 *ULN	>20.0 *ULN
Aspartate amino transferase ^c		>1-3 *ULN	>3-5 *ULN	>5-20 *ULN	>20 *ULN
Bilirubin (total) ^c		>1.0-1.5 *ULN	>1.5-3.0 *ULN	>3.0-10.0 *ULN	>10.0 *ULN
Calcium (ionized) low ^a	mmol/L	<LLN-1.0	<1.0-0.9	<0.9-0.8	<0.8
	mg/dL	<LLN-4.0	<4.0-3.6	<3.6-3.2	<3.2
Calcium (ionized) high ^a	mmol/L	>ULN-1.5	>1.5-1.6	>1.6-1.8	>1.8
	mg/dL	>ULN-6.0	>6.0-6.4	>6.4-7.2	>7.2
Calcium (corrected) low ^a	mmol/L	<LLN-2.00	<2.00-1.75	<1.75-1.50	<1.50
	mg/dL	<LLN-8	<8-7	<7-6	<6
Calcium (corrected) high ^a	mmol/L	>ULN-2.9	>2.9-3.1	>3.1-3.4	>3.4

Statistical Analysis Plan

ARGX-113-2010

Final analysis

Final 1.0 of 29APR2025

PARAMETER	Unit	GRADE 1	GRADE 2	GRADE 3	GRADE 4
Cholesterol ^a	mg/dL	>ULN-11.5	>11.5-12.5	>12.5-13.5	>13.5
	mmol/L	>ULN-7.75	>7.75-10.34	>10.34-12.92	>12.92
Creatine kinase ^c	mg/dL	>ULN-300	>300-400	>400-500	>500
		>1.0-2.5 *ULN	>2.5-5.0 *ULN	>5.0-10.0 *ULN	>10.0 *ULN
Creatinine ^c		>1.0-1.5 *ULN	>1.5-3.0 *ULN	>3.0-6.0 *ULN	>6.0 *ULN
Gamma-glutamyl transferase ^c		>1.0-2.5 *ULN	>2.5-5.0 *ULN	>5.0-20.0 *ULN	>20.0 *ULN
Glucose (fasting) low ^{a,b}	mmol/L	<LLN-3.0	<3.0-2.2	<2.2-1.7	<1.7
	mg/dL	<LLN-55	<55-40	<40-30	<30
Lipase ^c		>1.0-1.5 *ULN	>1.5-2.0 *ULN	>2.0-5.0 *ULN	>5.0 *ULN
Magnesium low ^a	mmol/L	<LLN-0.5	<0.5-0.4	<0.4-0.3	<0.3
	mg/dL	<LLN-1.2	<1.2-0.9	<0.9-0.7	<0.7
Magnesium high ^a	mmol/L	>ULN-1.23	-	>1.23-3.30	>3.30
	mg/dL	>ULN-3.0	-	>3.0-8.0	>8.0
Potassium low ^a	mmol/L	-	<LLN-3.0	<3.0-2.5	<2.5
	mEq/L	-	<LLN-3.0	<3.0-2.5	<2.5
Potassium high ^a	mmol/L	>ULN-5.5	>5.5-6.0	>6.0-7.0	>7.0
	mEq/L	>ULN-5.5	>5.5-6.0	>6.0-7.0	>7.0
Sodium low ^a	mmol/L	<LLN-130	-	<130-120	<120
	mEq/L	<LLN-130	-	<130-120	<120
Sodium high ^a	mmol/L	>ULN-150	>150-155	>155-160	>160
	mEq/L	>ULN-150	>150-155	>155-160	>160

Statistical Analysis Plan

ARGX-113-2010

Final analysis

Final 1.0 of 29APR2025

PARAMETER	Unit	GRADE 1	GRADE 2	GRADE 3	GRADE 4
Triglycerides	mmol/L	1.71-3.42	>3.42-5.70	>5.70-11.4	>11.4
	mg/dL	150-300	>300-500	>500-1000	>1000

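### On its plain reading, SAP 5.2.2 gives no laboratory flag to high glucose, white cells, neutrophils, platelets or albumin, contrary to the SAP's own glucose example

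*SAP*

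**What the plan says.** - **Low/Normal/High categories.** SAP 5.2.2 defines them against the laboratory's normal range and then limits their use: "Abnormalities will be derived for hematology and biochemistry parameters for which no toxicity grading is defined".
- **Toxicity grades.** The same section adds: "Only the parameters described in appendix 9.2 will be computed, according to the declared limits for each grade".
- **Table 8.** The only glucose entry is "Glucose (fasting) low". The white blood cell, neutrophil, platelet and albumin rows have limits below normal only. No hemoglobin row appears in the text available.
- **Treatment-emergent.** The SAP's Definition of Terms illustrates the concept with "hemoglobin normal or grade 1 at baseline and grade 2 postbaseline; glucose low at baseline and high postbaseline".
- **Displays.** Under SAP 5.2.3, Table 14.3.4.1.2 cross-tabulates abnormalities and Table 14.3.4.1.3 cross-tabulates grades, at last assessment and worst case. Listing 16.2.8.1 carries all laboratory data, but "only for participants with any postbaseline abnormality or toxicity grade" of at least 1.

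**The concern.** The exclusion in 5.2.2 is written for the parameter as a whole. A parameter graded in one direction therefore loses its Low/Normal/High categories in both, and nothing covers the ungraded direction. For five parameters the uncovered direction is the high one.

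Long-term safety is the primary objective. Protocol Table 3 names serious infection and complications of oral corticosteroids (OCS) as risks, and its mitigation for the latter includes "Continuously monitor safety, including glucocorticoid-mediated toxicity, throughout the study". High white cells or neutrophils and high glucose are relevant laboratory signals for those risks. If the worst-case tables cannot register them, those tables describe laboratory safety from one side only. A mid-study peak would also be missed by the descriptive tables, which show only baseline and last assessment.

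**Working it through.** There is no stated figure to reproduce: "No formal hypothesis testing will be conducted in this open-label study", and the point is about a derivation rule. The check applies the rule to the panel.

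**Inputs.** The panel in SAP 5.2.1 has 12 hematology and 20 biochemistry parameters (total and direct bilirubin counted separately), so 12 + 20 = 32. Graded directions come from Table 8.

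**Step 1: sort the 32 parameters.**
- No grading, so Low/Normal/High applies (15): RBC, hemoglobin, hematocrit, MCV, MCH, monocytes, basophils, eosinophils, direct bilirubin, BUN, CRP, HbA1c, total protein, HDL, LDL.
- Graded in both directions (4): lymphocytes, sodium, potassium, and calcium if it maps to the corrected or ionized rows. If it does not, calcium is ungraded and still covered on both sides.
- Graded low only (5): glucose, white blood cells, neutrophils, platelets, albumin.
- Graded high only (8): ALT, AST, ALP, total bilirubin, creatinine, GGT, cholesterol, triglycerides.

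Check: 15 + 4 + 5 + 8 = 32. One-direction parameters: 5 + 8 = 13.

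**Step 2: trace illustrative values through the rules.**
- Glucose 5.5 to 20 mmol/L: Table 8 has no high row, so no grade. Glucose is a graded parameter, so no High category. Result: not abnormal, not treatment-emergent, not worst case.
- White cells 7 to 25 giga/L: the same result for the same reason.
- Hemoglobin, with an assumed normal range of 120 to 160 g/L (not in the documents):
  - 130 to 100: Normal to Low, treatment-emergent.
  - 130 to 75: Normal to Low, treatment-emergent and displayed identically to the previous case.
  - 115 to 75: Low to Low, not treatment-emergent. This holds for any lower limit above 115. At 115 or below, the baseline is Normal and the shift is treatment-emergent.

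**Step 3: compare with the Definition of Terms.** The glucose example needs a High category for glucose, and the hemoglobin example needs grades for hemoglobin. Neither can be produced by 5.2.2 with Table 8 as provided.

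**Step 4: does parameter already mean parameter and direction?** SAP 2.2.5 treats them as separate terms: worst-case grades are "derived per parameter and toxicity direction (hypo/hyper"). SAP 5.2.3 likewise singles out parameters graded in both directions. The 5.2.2 note names only the parameter.

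**The case against.** The strongest case on the other side has four parts.

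- **Other routes remain.** A reader might infer that hyperglycaemia, leukocytosis and anaemia cannot appear as treatment-emergent laboratory findings at all. The documents do not support that. Hemoglobin, being ungraded, gets Low/Normal/High, so new anaemia is counted. High HbA1c and high CRP are categorised; high lymphocytes are graded; high monocytes, basophils and eosinophils are categorised. Infections are AESIs with their own tables (SAP 5.1), the GTI has an HbA1c and diabetic-medication domain (SAP 9.1.1.2), and clinically significant laboratory changes are recorded as AEs (Protocol 8.3.4). All of this stands and makes the loss partial. It does not replace the tables: HbA1c does not show individual glucose excursions, and AE recording depends on investigator judgment.
- **The listing filter works by participant.** Any other postbaseline flag lists all of that participant's laboratory data. As an illustration, assume a 5% flag rate for each of the 15 ungraded parameters at one visit: the chance of at least one flag runs from 5% (complete dependence) to 1 - 0.95^15 = 54% (independence), before counting further visits. So it would be wrong to say that high values go unlisted in general; only participants with no other flag are affected.
- **Table 8 labels the glucose row as low.** Someone could treat that label as the parameter name and derive a High category for glucose. This makes the rule arguable for glucose, but not for white cells, neutrophils, platelets or albumin, whose rows carry no direction label.
- **The appendix text is visibly damaged.** Table lists recur inside appendix 9.1, the blood pressure section is duplicated, and section 9.1.1.5 is missing. A lost hemoglobin row cannot be excluded, so that part is conditional on the source PDF.

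**Conclusion.** The point holds in limited form. As written, high values of five protocol-required parameters have no place in the abnormality or toxicity displays, and the SAP contradicts its own glucose example. Eight other parameters lose the low side, for which no particular need has been shown. If Table 8 truly has no hemoglobin row, deepening of an already low hemoglobin and all severity information are also missing, contrary to the SAP's hemoglobin example; normal-to-low shifts are not lost.

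This should be corrected, but it does not touch the primary endpoint, which rests on AEs, SAEs, AESIs and discontinuations for safety. The affected displays are descriptive. The conclusion assumes the plain reading of parameter in 5.2.2 and that Table 8 is complete as extracted. Confidence is highest for white cells, neutrophils, platelets and albumin, lower for glucose because of its row label, and conditional for hemoglobin.

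**What to change.** 1. Reword the 5.2.2 note so that Low/Normal/High is derived for each hematology and biochemistry parameter and direction that has no toxicity grading. This affects 13 parameters (5 high side, 8 low side). The sponsor may limit it to the high side of the five and say so.
2. Apply the same flags to the treatment-emergent counts, the worst-case visit and the trigger for Listing 16.2.8.1.
3. Check Table 8 in the source PDF for a hemoglobin row. If it is absent, add one from the CTCAE v5.0 that the SAP already applies; the grade limits are not in the documents and must be taken from that source.

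**Cost.** SAP text, possibly one Table 8 row, and extra rows in existing tables. No new data are needed, since laboratory normal ranges are already available (SAP 5.2.1). The downsides are somewhat longer tables and some non-fasting high glucose values being flagged, which a footnote can explain.

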5.2.3 Presentation of results

The SAF analysis set will be used for the clinical laboratory evaluation. For tables by analysis visit, only the baseline and last assessment analysis visits will be shown. Cross-tabulations will also include the worst-case analysis visit. All other analysis visits will be included in listings.

Only continuous laboratory parameters expected per protocol will be tabulated, except for INR. The statistical analysis will present results in standardized units, except for creatinine clearance (adjusted for BSA), which will be reported in mL/min/1.73m².

Continuous laboratory parameters will be summarized using descriptive statistics at each analysis visit of interest. Actual values and changes from study baseline will be shown in the same table.

Laboratory abnormalities will be presented as cross-tabulations of the abnormality at each postbaseline analysis visit of interest versus the study baseline abnormality. The number of participants with treatment-emergent abnormalities will also be shown (see Definition of terms). The denominator for the percentage is the total number of

	Statistical Analysis Plan	
ARGX-113-2010	Final analysis	Final 1.0 of 29APR2025

participants with nonmissing data for the parameter and analysis visit in the SAF analysis set.

Laboratory toxicity grades will be presented as cross-tabulations of the toxicity at each postbaseline analysis visit of interest versus the study baseline toxicity. Numbers and cumulative numbers over decreasing toxicity grading of participants with treatment-emergent toxicities will also be shown. The denominator for the percentage is the total number of participants with nonmissing data for the parameter and analysis visit in the SAF analysis set. Parameters with toxicity grades defined in both directions (hypo and hyper) will be shown by direction.

All laboratory data will be listed for the ROL analysis set, including laboratory tests not foreseen per protocol, but only for participants with any postbaseline abnormality or toxicity grade ≥ 1 .

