In ARGX-113-2009, participants received efgartigimod PH20 SC or placebo with concurrent OCS, or rescue therapy (without efgartigimod PH20 SC or placebo). When rolling over to ARGX-113-2010, participants will either initiate or continue efgartigimod PH20 SC treatment, while maintaining the blinded treatment allocation of ARGX-113-2009 (refer to Section 6.4).

Before protocol amendment 2, participants had to stop receiving efgartigimod PH20 SC upon achieving CR or PR while off concurrent BP therapy for ≥ 8 weeks. After protocol amendment 2, participants who stopped efgartigimod PH20 SC will reinstate treatment at the investigator's discretion. If they relapse, reinstatement of efgartigimod PH20 SC treatment is mandatory. All other participants (ongoing and newly enrolled) will continue to receive efgartigimod PH20 SC until the end of the treatment period. Concurrent BP therapies, including rescue therapies started during ARGX-113-2009, will be tapered or discontinued. IMP will be permanently discontinued if the investigator considers it not to be in the participant's best interest to taper or discontinue rescue therapy or initiate efgartigimod PH20 SC.

Brief Summary: The purpose of this study is to evaluate the safety of efgartigimod PH20 SC over a longer period of time in adult participants with moderate-to-severe BP. The study will also evaluate the efficacy of efgartigimod PH20 SC.

Health Measurement/Outcome: The primary outcome measure is the long-term safety and tolerability of open-label efgartigimod PH20 SC for approximately 1 year after completing ARGX-113-2009.

Investigational Medicinal Product and Investigational Medicinal Product Formulation:

Efgartigimod PH20 SC [REDACTED]

Condition/Disease: Bullous pemphigoid

Study Duration: Approximately 56 weeks

Treatment Duration: Up to 48 weeks

Visit Frequency: Participants will visit the site at weeks 0 (baseline), 1, 2, 4, and 8. After that, participants will visit every 4 weeks. Participants not receiving efgartigimod PH20 SC will visit every 8 weeks. A treatment-free period of 8 weeks follows the EoTP visit at week 48, with visits at EoTP + 4 weeks (if receiving efgartigimod PH20 SC) and EoTP + 8 weeks.

Number of Participants: All participants who complete the EoTP visit (week 36) in ARGX-113-2009 and meet the eligibility criteria can roll over to this study. All participants rolling over agree to participate in the clinical study by completing the informed consent process.

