4.4. End-of-the-Study Definition

The end of the study is defined as the date of the last participant's last visit.

A participant is considered to have completed the study if the follow-up visit at EoTP + 8 weeks has been completed.

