2. GENERAL METHODOLOGY

2.1 ANALYSIS SETS

2.1.1 *Analysis sets*

The following participant analysis sets (PAS) will be used:

Rollover (ROL) analysis set: All participants who rolled over from ARGX-113-2009 and provided informed consent for participation in ARGX-113-2010

Safety (SAF) analysis set: All participants from the ROL analysis set who received at least one dose of IMP

Notes:

- Provided informed consent is defined as having a complete informed consent signature date in the database.
- Received at least one dose of IMP is defined as having an exposure date or any information confirming exposure present in the database.

2.1.2 *As planned versus as actual analysis*

Not applicable. All endpoints will be analyzed for the total group of participants, regardless of previous treatment in ARGX-113-2009 (placebo or efgartigimod PH20 SC).

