Adverse events will be allocated to phases as described in section 5.1.2. Concomitant therapies and procedures will be allocated to phases and (sub)periods as described in section 3.3.2. All other assessments will be allocated to phases and (sub)periods based on the assessment date/time. In case of (partially) missing date/time fields disabling allocation of an assessment to phases or (sub)periods, information from the visit label, time point label and the protocol schedule of activities will be used to allocate to the correct phase.

For efficacy assessments without time part, an assessment on the day of switch from observation phase to treatment phase will be considered as part of the treatment phase. Likewise, an assessment on the day of switch from treatment period 1 to treatment period 2 will be considered as part of treatment period 2.

2.2.2 *Baseline and change from baseline*

Study baseline is defined as the first available and nonmissing value at the baseline visit (scheduled or unscheduled) in ARGX-113-2010. This value corresponds with the value at the EoTP visit in ARGX-113-2009 (and is copied over into the database of ARGX-113-2010 at SDTM level).

Change from baseline is defined as:

- Change from baseline at time point t = value at time point t – baseline value.

Percentage change from baseline at time point t is defined as follows:

- When baseline value is not zero: $100 * ((\text{value at time point } t - \text{baseline value}) / \text{baseline value})$
- When both baseline value and value at time point t are zero: 0
- When baseline value is zero and value at time point t is not zero: not calculated

For immunogenicity assessments, the study baseline selection will be performed by sample (not by parameter) in order to keep the ADA and NAb results of a sample together. Furthermore, values resulting in an unevaluable ADA status are given the lowest priority when the selection is made.

For evaluation of PD parameters, a treatment period-specific baseline (TPnB) will be defined:

	Statistical Analysis Plan	
ARGX-113-2010	Final analysis	Final 1.0 of 29APR2025

- For a treatment period, TPnB is the last available and non-missing value prior to the first IMP administration in the treatment period. Assessments on day 1 of a treatment period without time collection or with time information exactly equal to the time of first IMP administration and which are planned predose will be considered as predose.

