All nonmissing postbaseline values on or after the first administration of IMP in ARGX-113-2010 and up to and including 60 days after the last IMP administration before the assessment will be considered when deriving the worst-case analysis visit. This may include unscheduled assessments, assessments not selected for the analysis visit and assessments during the follow-up phase.

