2.2.6 Last assessment

A last assessment analysis visit will be created as the last available postbaseline assessment with a nonmissing value.

The last assessment will be created for the following parameters:

- BPDAI total and activity score
- IGA-BP
- Itch NRS 24-hour average and worst scores
- ABQOL, DLQI and EQ-5D-5L questionnaires
- GTI AIS and CWS
- Numeric parameters of safety lab, vital signs and ECG

For PD parameters, a last assessment analysis visit will be created per treatment period as the last available post-TPnB assessment with a nonmissing value in the treatment period. Assessments during the follow-up phase will be considered in the selection of the last assessment of the preceding treatment period.

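### For study completers, the laboratory and vital signs mean-change tables compare baseline with an off-drug follow-up value, so they do not describe change under treatment

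*SAP*

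**What the plan says.** - **Visits shown.** SAP 5.2.3, on laboratory results: "For tables by analysis visit, only the baseline and last assessment analysis visits will be shown". SAP 5.3.3 has the same rule for vital signs. The worst-case visit is added to the cross-tabulations only. Other visits go to listings.
- **Last assessment.** SAP 2.2.6: "A last assessment analysis visit will be created as the last available postbaseline assessment with a nonmissing value". The parameters covered include "Numeric parameters of safety lab, vital signs and ECG". No phase or time since dosing is specified.
- **Worst case, for contrast.** SAP 2.2.5 counts values from the first dose in this study "up to and including 60 days after the last IMP administration before the assessment will be considered when deriving the worst-case analysis visit".
- **Baseline.** SAP 2.2.2: "This value corresponds with the value at the EoTP visit in ARGX-113-2009".
- **Pooling.** SAP 2.1.2 analyzes one total group whatever the prior arm. SAP 2.4.2 gives the safety set a single efgartigimod label.
- **Follow-up.** Protocol 1.1: "A treatment-free period of 8 weeks follows the EoTP visit at week 48". Protocol 4.4: "A participant is considered to have completed the study if the follow-up visit at EoTP + 8 weeks has been completed". The schedules of activities call for chemistry, hematology and vital signs at that visit. ECGs are not scheduled in follow-up, so the ECG tables do not share the problem by design.

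**The concern.** The primary objective is the long-term safety of treatment. A table of laboratory or vital signs change under the efgartigimod label, titled as running over time, invites the reader to take its mean change as change on treatment. For a completer with a follow-up result, the endpoint of that change is a value taken after dosing has stopped. The starting point is on drug for some participants and off drug for others, so the pooled mean mixes on-to-off changes with off-to-off changes. Neither is a change under treatment.

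Albumin and total protein are the plausible cases. Protocol 6.4 keeps both blinded through week 4, which suggests that the sponsor expects treatment to move them. Protocol 8.4.6 states that the drug lowers IgG, which is part of total protein. A shift that stays within the normal range would not show in the abnormality cross-tabulations, so the mean-change table is where one would look for it.

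**Working it through.** The plan states no figure to reproduce. The check traces the selection rule and then asks what the pooled mean change can look like.

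**Timing** (SAP Table 3 convention: target day = 7 × week + 1; visit window ±3 days at EoTP + 8 weeks)

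- Week 48: 7 × 48 + 1 = day 337. EoTP + 8 weeks: 337 + 56 = day 393.
- Last dose at week 48, the latest allowed: 393 - 337 = 56 days, or 53 to 59 with the window. This is inside the 60-day limit used for the worst case.
- Last dose at week 47 (day 330): 393 - 330 = 63 days, outside that limit.
- Stop at week 12 under protocol v2.0 without restart (day 85): 393 - 85 = 308 days.

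**Pooled mean change.** Let d be the on-drug shift in a parameter (either sign), p the share on drug at baseline, s the share on drug at week 48, and r the share of the shift gone by EoTP + 8 weeks. Assume that participants off drug at baseline or at week 48 carry no shift, and that every last value is the follow-up sample. Then:

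- change at week 48 = (s - p)d
- change at last assessment = (s(1 - r) - p)d

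The sign reverses when s > p and r > 1 - p/s. With s = 1 this is r > 1 - p. The documents give none of d, p, s or r, so the values below are assumptions.

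| s | p | Week 48 | Last, r = 0.5 | Last, r = 0.75 | Last, r = 1 |
|---|---|---|---|---|---|
| 1 | 0.4 | +0.60d | +0.10d | -0.15d | -0.40d |
| 1 | 0.5 | +0.50d | 0 | -0.25d | -0.50d |
| 1 | 0.6 | +0.40d | -0.10d | -0.35d | -0.60d |
| 0.8 | 0.5 | +0.30d | -0.10d | -0.30d | -0.50d |
| 0.6 | 0.6 | 0 | -0.30d | -0.45d | -0.60d |

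In the last row nothing reverses, because the week 48 change is zero, but a change produced by stopping the drug appears.

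**Not every last value is a follow-up sample.** A missing result falls back to an earlier visit, and a withdrawn participant's last value may come from an early discontinuation visit close to dosing. If a share c of last values are follow-up samples, the rest are on drug and s = 1, the change is (1 - cr - p)d. With p = 0.5 and r = 1:

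- c = 0.9: 1 - 0.9 - 0.5 = -0.40d
- c = 0.8: 1 - 0.8 - 0.5 = -0.30d
- c = 0.6: 1 - 0.6 - 0.5 = -0.10d

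With p = 1/3, r = 0.5 and c = 1, the change is 1 - 0.5 - 0.33 = +0.17d, against +0.67d at week 48: diluted, not reversed.

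**Do other outputs fill the gap?** Tables 14.3.4.1.2, 14.3.4.1.3 and 14.3.4.2.2 include the worst case, which covers on-treatment values, but they count categories or grades. Albumin is graded in SAP 9.2; total protein is not graded there and is classed low, normal or high under SAP 5.2.2. Listings 16.2.8.1 and 16.2.8.2 cover only participants with a postbaseline abnormality (or, for laboratory data, a toxicity grade of at least 1). No planned table gives an on-treatment postbaseline mean or mean change for these completers.

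**The case against.** The strongest case against is that this is a presentation matter. Laboratory and vital signs means are not an endpoint at any level. Protocol 8.3.4 requires clinically significant laboratory changes to be recorded as adverse events, so they reach the primary tables. Protocol 9.3.1 promises only descriptive laboratory and vital signs analysis. The column is defined as the last assessment, and after a week 48 dose the follow-up sample lies inside the SAP's own 60-day window. All of this stands and limits the weight of the point. It does not make the column an on-treatment one.

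A reader might infer that no on-treatment laboratory value is summarized anywhere. The documents do not support that. The worst-case cross-tabulations are planned tables that cover the treatment period, and the baseline of participants still dosed with efgartigimod in ARGX-113-2009 is itself on drug.

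A reader might also infer that the sign of the mean change will reverse, or that pooling alone causes it. That is not supported either. Reversal needs a drug effect, enough washout and more participants on drug at week 48 than at baseline. It arises from an on-drug baseline set against an off-drug endpoint; pooling carries it into one mean and hides it. No document shows an effect on most parameters in these tables.

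**Conclusion.** The point holds as a gap in two descriptive tables. For completers with a nonmissing EoTP + 8 weeks result, the tabulated change ends at a value taken at least 53 days after the last dose and starts from a baseline of mixed drug status. This follows from the plan's own rules and its visit schedule. It does not describe change under treatment.

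The size for any parameter is unknown. Dilution or reversal is possible where the drug shifts a parameter and the shift fades by follow-up, with total protein and albumin the plausible candidates. The documents give neither the shift, the shares on drug, nor the washout. What is missing is the on-treatment mean and mean change. Treatment-emergent adverse events, discontinuations for safety and worst-case abnormality counts do not change. It is a modest point, worth acting on because the correction is cheap and serves the primary safety objective.

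**What to change.** In SAP 2.2.6, define a last on-treatment assessment for safety laboratory and vital signs parameters: the last nonmissing value after the first IMP dose in this study and within a stated short window after the last IMP dose. Fourteen days is a reasonable example (one 7-day dosing interval plus the 7-day visit window), but the length is a choice. Show it next to baseline in Tables 14.3.4.1.1 and 14.3.4.2.1. Keep the existing last assessment and label it as including follow-up.

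Optionally, show the changes by prior ARGX-113-2009 arm, which SAP 4.1.2 already uses. Prior arm is not the same as being on drug at baseline, because participants may have discontinued or interrupted IMP before rollover. A split by actual drug status would also need the ARGX-113-2009 dosing records.

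The cost is SAP wording and one added column in two tables, from data already collected. Participants with no sample in the window will be missing from the new column, and any split has smaller numbers per group.
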